5.5. Investigational Product Storage

The investigator or an approved representative, eg, pharmacist, will ensure that all investigational products are stored in a secured area with controlled access under required storage conditions and in accordance with applicable regulatory requirements.

Investigational products should be stored in their original containers and in accordance with the labels.

Any storage conditions stated in the SRSD will be superseded by the storage conditions stated on the product label.

Site systems must be capable of measuring and documenting (for example, via a log), at a minimum, daily minimum and maximum temperatures for all site storage locations (as applicable, including frozen, refrigerated, and/or room-temperature products). This should be captured from the time of investigational product receipt throughout the study. Even for continuous-monitoring systems, a log or site procedure that ensures active evaluation for

excursions should be available. The intent is to ensure that the minimum and maximum temperature is checked each business day to confirm that no excursion occurred since the last evaluation and to provide the site with the capability to store or view the minimum/maximum temperature for all non-working days upon return to normal operations. The operation of the temperature monitoring device and storage unit (for example, refrigerator), as applicable, should be regularly inspected to ensure they are maintained in working order.

Any excursions from the product label storage conditions should be reported to Pfizer upon discovery. The site should actively pursue options for returning the product to the storage conditions described in the labeling, as soon as possible. Deviations from the storage requirements, including any actions taken, must be documented and reported to Pfizer.

Once an excursion is identified, the investigational product must be quarantined and not used until Pfizer provides permission to use the investigational product. It will not be considered a protocol deviation if Pfizer approves the use of the investigational product after the temperature excursion. Use of the investigational product prior to Pfizer approval will be considered a protocol deviation. Specific details regarding information the site should report for each excursion will be provided to the site.

Site staff will instruct patients on the proper storage requirements for take home investigational products.

5.6. Investigational Product Accountability

The investigator site must maintain adequate records documenting the receipt, use, loss, or other disposition of the investigational product supplies. All investigational products will be accounted for using a drug accountability form/record.

All bottles of study drug must be returned to the investigator by the patient at every visit and at the end of the trial.

5.6.1. Destruction of Investigational Product Supplies

The sponsor or designee will provide guidance on the destruction of unused investigational product (eg, at the site). If destruction is authorized to take place at the investigator site, the investigator must ensure that the materials are destroyed in compliance with applicable environmental regulations, institutional policy, and any special instructions provided by Pfizer, and all destruction must be adequately documented.

5.7. Concomitant Treatments

All information on concomitant treatment (medications or procedures) must be recorded on the patient's eCRF (including the name or the medication or procedure and duration of treatment).

If there is a clinical indication for one of these or other medications specifically prohibited during the trial, discontinuation from study therapy or medication may be required. The final decision on any supportive therapy rests with the investigator and/or the patient's primary

physician. However, the decision to continue the patient on study therapy or medication schedule requires the mutual agreement of the investigator, the sponsor, and the patient.

Concomitant treatment considered necessary for the patient's well-being may be given at the discretion of the treating physician.

Concomitant medications and treatments will be recorded from 28 days prior to the registration and up to 28 days after the last dose of study treatment. All concomitant medications should be recorded in the CRF including supportive care drugs (eg, antiemetic treatment and prophylaxis), and the drugs used to treat AEs or chronic diseases, and non-drug supportive interventions (eg, transfusions).

There are no prohibited therapies during the Long-Term Follow-Up Phase.

5.7.1. Prohibited Medications

- Any concurrent chemotherapy, radiotherapy, or anticancer immunotherapy other than as defined in this protocol.
- Any other anti-cancer therapy.
- Any other investigational agents.
- Drugs known to prolong the QT interval or predispose to Torsades de Pointes (see [Appendix 4](#)).
- Concurrent anticoagulation therapy with warfarin or related oral anticoagulant therapy. Concurrent therapeutic anticoagulation with low molecular weight heparin will be permitted.
- Prophylactic use of growth factors.

5.7.2. Permitted Medications

- Any medication (other than those prohibited above or per inclusion/exclusion criteria) for a concurrent medical condition is permitted.
- Treatment of diarrhea and other GI symptoms will be optimized.
- Treatment with growth factors, eg, for neutropenia (including granulocyte colony-stimulating factor [G-CSF] according to American Society of Clinical Oncology [ASCO] guidelines).
- Supplementation is advised for potassium levels or magnesium levels below the LLN, with consideration of the patient's underlying renal function.

- Up to 6 months of prior hydroxyurea is permitted prior to signature of informed consent document. Hydroxyurea is also permitted during the first 21 days of study treatment following registration.
- Temporary steroid use will be permitted for treatment of AEs – limited to systemic steroids for no more than 10 days and at doses ≤ 60 mg prednisone/day or the equivalent. Of note, inhaled and topical steroids are permitted without limitation.

5.7.3. Other Treatment Considerations: Interaction with Other Medical Products and Other Forms of Interaction

The concomitant use of bosutinib with strong or moderate cytochrome P450 (CYP3A) inhibitors (reference [Appendix 5](#)) should be avoided, as an increase in bosutinib plasma concentration may occur.

If a strong or moderate CYP3A inhibitor must be administered during bosutinib treatment, an interruption of bosutinib therapy and/or a dose reduction in bosutinib should be considered. Patients should also be strongly encouraged to avoid herbal remedies. Grapefruit and grapefruit juice should also be avoided.

The concomitant use of bosutinib with strong or moderate CYP3A inducers including St. John's Wort should be avoided ([Appendix 5](#)); it is not recommended as it will significantly reduce exposure to bosutinib.

Bosutinib should be used with caution in patients who have or may develop QT interval prolongation, including those patients taking anti-arrhythmic medicinal products (see [Appendix 4](#)).

Inhibitors of platelet aggregation, ie, aspirin, dipyridamole, clopidogrel, and ticlopidine, should be used with caution.

Transfusions for anaemia or thrombocytopenia may only be given in the interest of patient safety. Transfusions will not be permitted in order to allow continued dosing of bosutinib when there is an indication for treatment interruption as outlined in the Dose Adjustment/Treatment Interruption tables (see [Table 2](#) and [Table 3](#)).

Caution should be exercised when administering bosutinib concomitantly with proton-pump inhibitors (PPIs). Short-acting antacids should be considered as an alternative to PPIs and administration times of bosutinib and antacids should be separated by at least 2 hours (eg, take bosutinib in the morning and antacids in the evening) whenever possible.

6. STUDY PROCEDURES

As applicable, all visits must occur within the predefined time windows outlined in this protocol.

6.1. Screening

Informed consent must be obtained prior to undergoing any study specific procedures.

For screening procedures, see [SCHEDULE OF ACTIVITIES](#) table and [ASSESSMENTS](#) section.

6.1.1. Collection of Banked Biospecimen

Collect a genomic banked biospecimen. If missed, collect at the next available time point when biospecimens are being collected in conjunction with a patient visit.

Blood will be collected at screening and retained in a Biobank for exploratory biomarker assessments, unless prohibited by local regulation or by the IRB/EC.

6.2. Core Treatment Phase

For Core Treatment Phase procedures, see [SCHEDULE OF ACTIVITIES](#) table and [ASSESSMENTS](#) section.

Patients will have visits at the study site on Day 1 and Weeks 1, 2, 3, 4, 6, 8, 10, 12, 16, 20, and 24, then every 12 weeks for the first year of treatment in the 12 months (48 weeks Core Treatment Phase). Additional visits may be required for patients requiring dose increases at the Week 12 and Week 24 visits, these will be performed as soon as possible and within 4 weeks of the result requiring dose change being known. Patients not requiring a dose change will be contacted by telephone.

6.3. Extension Phase

For Extension Phase procedures, see [SCHEDULE OF ACTIVITIES](#) table and [ASSESSMENTS](#) section.

All patients will be treated and/or followed up to approximately 3 years (144 weeks) after registration of the last patient or study termination. Patients who discontinue study therapy early due to disease progression or intolerance to study medication will continue to be followed for survival for up to approximately 3 years (144 weeks) after registration of the last patient or until study termination.

If a patient does not return for a scheduled visit, every effort should be made to contact the patient. All attempts to contact the patient and information received during contact attempts must be documented in the patient's medical record. In any circumstance, every effort should be made to document patient outcome, if possible. The investigator should inquire about the reason for withdrawal, request the patient to return all unused investigational products, request that the patient return for a final visit, if applicable, and follow up with the patient regarding any unresolved AEs.

If the patient refuses further visits, the patient should continue to be followed for survival. If the patient withdraws from the study, and also withdraws consent for disclosure of future information, no further evaluations should be performed, and no additional data should be collected. The sponsor may retain and continue to use any data collected before such withdrawal of consent.

6.4. End of Treatment/Withdrawal Visit

For End of Treatment/Withdrawal visit procedures, see [SCHEDULE OF ACTIVITIES](#) table and [ASSESSMENTS](#) section.

Patients who discontinue from study treatment for any reason should complete an End of Treatment/Withdrawal visit between 7 and 28 days after the last dose of study drug, and the patient enters Long-Term Follow-Up.

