The investigator may schedule visits (unplanned visits) in addition to those listed in the SCHEDULE OF ACTIVITIES table in order to conduct evaluations or assessments required to protect the well-being of the patient.

Visit Identifier ^a	Screening		Core Treatment Phase													Extension Phase	End of Treatment / Withdrawal
	0	0	1	1	1	1	1	2	2	3	3	4	5	6	9, 12		
Month	0	0	1	1	2	3	4	6	8	10	12	16	20	24	36, 48	Every 12 weeks up to 2 years, then every 24 weeks thereafter	7-28 days after the last dose of study drug
Week	0	0	1	1	2	3	4	6	8	10	12	16	20	24	36, 48		
Day	-28 to registration	-14 to registration	1	7	14	21	28	42	56	70	84	112	140	168	252, 336		
Visit Time Window			±4 days													±1 week	
Informed consent	X																
Registration			X														
Inclusion/Exclusion criteria review	X																
Demographic data collection		X															
Sokal score calculation ^b		X															
Medical ^c /Cancer history ^d review		X															
Physical examination ^e		X				X		X		X					X	X	X
Vital signs, weight, and height (screening only) ^f		X	X							X				X	X	X	X
ECOG performance status		X								X						X	X
Extramedullary assessment ^g		X				X		X		X					X	X	X
Digital ECG ^h		X	X			X		X		X						As clinically indicated	
Chest X-ray		X								As clinically indicated							X
Contraception check ^l	X		X			X		X		X	X	X	X	X	X	X	X
ECHO or MUGA ^l	X									As clinically indicated							X

Visit Identifier ^a	Screening		Core Treatment Phase													Extension Phase	End of Treatment / Withdrawal
	0	0	1	1	1	1	1	2	2	3	3	4	5	6	9, 12		
Month	0	0	1	1	2	3	4	6	8	10	12	16	20	24	36, 48	Every 12 weeks up to 2 years, then every 24 weeks thereafter	7-28 days after the last dose of study drug
Week	0	0	1	1	2	3	4	6	8	10	12	16	20	24	36, 48		
Day	-28 to registration	-14 to registration	1	7	14	21	28	42	56	70	84	112	140	168	252, 336		
Visit Time Window			±4 days													±1 week	
Laboratory Tests																	
Hematology including CBC with differential ^k		X		X	X	X	X	X	X	X	X	X	X	X	X	X ^y	X
Chemistry panel with electrolytes and CK ^l		X				X		X		X		X	X	X	X ^y	X	
Liver function tests ^m		X				X		X		X		X	X	X	X ^y	X	
Estimated glomerular filtration rate		X				X		X		X		X	X	X	X ^y	X	
Coagulation panel ⁿ		X								X					X ^y	X	
HBV and HCV test		X															
Dipstick urinalysis (microscopic if abnormalities detected)		X				X				X					X ^y	X	
Serum or urine pregnancy test (for women of childbearing potential)	X		X			X		X		X	X	X	X	X	X ^y	X	

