- b. Every effort should be made in order to have Sokal score calculated prior to any anti-CML treatments (ie. at initial diagnosis of patient). Sokal formula is $Exp(0.0116 \times (age - 43.4) + 0.0345 \times (spln - 7.51) + 0.188 \times [(plt/700)^2 - 0.563] + 0.0887 \times (blasts - 2.1))$; Note: Spln=centimeters below costal margin, plt=platelet count, $10^9/L$, blasts=% blasts in peripheral blood. If the patient has already received anti-CML treatment prior to screening every effort should be made to obtain test results/data before the start of treatment in order to calculate the Sokal score. If patient did not have prior anti-CML treatment, the Sokal score will be calculated using data obtained at screening.
- c. Medical history review includes clinically significant past and current diagnoses (including complete cardiac history) and surgical procedures.
- d. Cancer history review includes full history of the course of the patient's cancer including date of diagnosis and any prior treatments, history of blood and platelet transfusions or history of lumbar punctures within 28 days prior to registration.
- e. Complete physical examination ensuring examination of liver and spleen will be performed.
- f. Vital signs include temperature (axillary), supine blood pressure, and heart rate. Height will be measured at screening only.
- g. Extramedullary assessment will include physical examination and based on this assessment and any specific evidence, appropriate imaging testing can be requested by the investigator. The assessment should be done at any time if extramedullary disease is suspected.
- h. Digital ECGs to be done in triplicate at each time point and should be performed at the same as PK sampling (if applicable). End of Treatment/Withdrawal visit ECG should be done at least 5 days after the last dose of bosutinib and prior to initiating other anticancer treatment (if possible). ECG should also be performed if clinically significant decrease in ejection fraction is detected by ECHO/MUGA while on treatment, and otherwise as clinically indicated.
- i. Male patients who are able to father children and female patients who are of childbearing potential will need to follow the contraception guidelines in Section 4.3.

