9.2.2. Analysis of Secondary Endpoints

9.2.2.1. Other Measures of MMR

Evaluations of MMR by 12 and 18 months will be assessed using the frequency tables. The 90% CI will also be calculated.

For the analysis of MMR by 12 and 18 months, a patient is counted as a responder if MMR occurs at or before 12 and 18 months, respectively, even if MMR is subsequently lost at or before the 12- or 18-month time point. A patient never achieving MMR at or before 12 and 18 months will be considered a non-responder, respectively.

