9.2.2.3. Duration of Response

The analysis of secondary endpoints relating to duration of response, such as duration of MMR and CCyR will be based on the estimations of the quartiles of duration and yearly rates using the Kaplan-Meier method. For the analysis of CCyR, the proportion of patients who have confirmed loss of response will also be evaluated.

The duration is measured from the first date of response until the first date of confirmed loss of response, treatment discontinuation due to progressive disease, or death due to disease

progression within 28 days after last dose. An unconfirmed loss followed by treatment discontinuation due to suboptimal response is considered a confirmed loss. Duration of response will be counted while a patient is on treatment and 28 days after last dose. If loss of response has not occurred, the patient will be censored at the last valid assessment.

The duration of MMR will be analyzed for the modified as-treated population and as-treated population separately. The duration of CCyR will be calculated using the modified as-treated population.

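### End of Treatment PCR and marrow samples need not precede a new anti-CML drug, and the by-12- and by-18-month response rules would still count them as bosutinib response

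*Protocol*

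**What the plan says.** **Timing of the samples.** Protocol 6.4 sets the End of Treatment "visit between 7 and 28 days after the last dose of study drug, and the patient enters Long-Term Follow-Up". The Schedule of Activities puts central PCR and mutation analysis at that visit. Marrow is conditional: under footnote p it is needed only if the previous aspirate is more than 12 weeks old and treatment did not end for cytogenetically confirmed failure.

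**Order relative to new therapy.** Footnote h asks for the End of Treatment ECG "prior to initiating other anticancer treatment (if possible". Footnotes p, s and t (marrow, PCR, mutation) and Sections 7.1.1 to 7.1.1.2 carry no such request.

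**New therapy.** Section 5.7.1 bars other anticancer therapy on study treatment. After discontinuation, Section 5.7 states: "There are no prohibited therapies during the Long-Term Follow-Up Phase". Footnote u and Section 8.1.4.2 foresee a new anticancer therapy starting inside the 28-day safety window.

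**Counting rules.**
- Protocol 9.2.2.1: "a patient is counted as a responder if MMR occurs at or before 12 and 18 months". SAP 6.2.1 says the same, and Protocol 9.2.2.2 and SAP 6.2.2 treat CCyR by 12 months alike. None of them limits counting to on-treatment or pre-switch samples.
- SAP 5.3.2 imputes CCyR on a date with MMR when no marrow cytogenetics are available.
- Protocol 9.3.1.2 and SAP 6.3.3 make discontinuation without response the competing event in time to response.
- Protocol 9.2.2.3: "Duration of response will be counted while a patient is on treatment and 28 days after last dose". SAP 3.2.3 instead censors duration at the last valid assessment on treatment.

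**The concern.** In a single-arm trial no control group offsets a response credited to the wrong drug. The plan recognises that a new therapy may start before the End of Treatment visit and protects the ECG against it, but not the samples that define response. Read literally, the by-12- and by-18-month rules then accept a post-switch sample as bosutinib response.

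The endpoints also contradict each other: the same patient can be a responder in MMR by 12 months and a non-responder with a competing event in time to MMR. At stake are MMR by 12 and 18 months and CCyR by 12 months (all secondary), the clarity of duration of response, and, in a narrow case, the Week 48 primary endpoint.

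**Working it through.** **1. How one patient is counted (hypothetical dates).** Week 12 PCR and marrow on day 84, no MMR or CCyR. Last dose day 120. New drug day 122. End of Treatment visit day 148 (120 + 28), with a first MMR.
- Exposure to the next drug at sampling: 148 − 122 = 26 days.
- Marrow: 148 − 84 = 64 days since the last aspirate, under 12 weeks (84 days), so none is required.
- MMR by 12 months: day 148 is before day 336, so a responder.
- CCyR by 12 months: no marrow result and MMR on that date, so CCyR is imputed and again a responder.
- Time to MMR and to CCyR: discontinuation without response came first, so the competing event has occurred.

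One sample therefore enters two response rates and is excluded from the two matching time-to-response analyses.

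**2. Largest influence of the next drug.** If it starts the day after the last dose, exposure is 7 − 1 = 6 days at a day-7 visit and 28 − 1 = 27 days at a day-28 visit.

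**3. Size per patient.** With N = 60, one misclassified responder adds 1/60 = 1.7 percentage points and two add 3.3. The documents give neither a discontinuation rate for this trial nor the share of patients who switch before the visit, so the number affected cannot be derived.

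**4. Reach into the primary endpoint.** SAP 7.2.1.4.1 uses day 332 = 336 − 4 for 12 months. Assuming a symmetric ±4-day window (days 332 to 340), an End of Treatment visit falls inside it only if the last dose was between day 332 − 28 = 304 and day 340 − 7 = 333, a span of 30 days. Assuming a proportion d of patients stops by Week 48, uniformly over time, the expected number is 60 × d × 30/336:

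| d (assumed) | Patients of 60 |
|---|---|
| 10% | 0.5 |
| 20% | 1.1 |
| 30% | 1.6 |

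These are upper limits: each patient must also switch before the visit, be in MMR at it, and have that sample assigned to Week 48.

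**5. What one such patient would do to the test.** Plan's figure (Protocol 9.1): power 82.1% for N = 60, 25% versus 40%, one-sided 5%.
- Normal approximation: Φ[(0.40 − 0.25 − 1.645 × √(0.25 × 0.75/60)) / √(0.40 × 0.60/60)] = Φ[(0.15 − 0.0919)/0.0632] = 82.07%. The critical count is 60 × (0.25 + 0.0919) = 20.5, hence 21 responders. The plan's figure is reproduced.
- Exact binomial for at least 21 of 60: power 82.1%, type I error 5.4%.
- If one counted responder were always a post-switch response, 20 bosutinib responders would suffice and the exact type I error at 25% would be 9.2%. With two it would be 14.9%.

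Step 5 shows sensitivity only; step 4 shows how unlikely the situation is.

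**The case against.** Several stronger readings are tempting, and the documents do not support them.

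- **That sites are forbidden to sample before day 7.** Section 6.4 says the visit should fall in that window, and the Schedule of Activities adds: "The investigator may schedule visits (unplanned visits) in addition to those listed". The stated purpose there is patient well-being, so nothing directs a site to sample before a switch, but earlier sampling is not barred. A patient who switches on or after day 7 could be sampled first within the window.
- **That End of Treatment results simply measure the next drug.** At most about 27 days of it follow the whole bosutinib course, so attribution is mixed.
- **That the primary endpoint is compromised.** Protocol 9.2.1 and SAP 6.1.1.1 require response at the 48-week visit. SAP 5.3.1.1 makes a missing Week 48 assessment a non-response unless Weeks 36 and 60 both show response. No text maps the End of Treatment visit to Week 48.
- **That duration of response is generally distorted.** SAP 3.2.3 censors at the last on-treatment assessment, and discontinuation due to progression counts as loss whatever the sample shows. What stands is ambiguity: the protocol adds 28 days, and SAP 6.2.4 points to a 28-day meaning of on treatment in SAP 6.3.5.
- **That failure mutations go unseen.** Section 5.4.1 also asks for mutation testing on the sample showing lack of optimal response, where possible.
- **That the count is large.** The 37% discontinuation in the earlier first-line trial (Protocol 1.2.3) would give 60 × 0.37 = 22 patients. It is a 24-month figure at a 500 mg starting dose, and it counts samples, not changed classifications.

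Two further arguments deserve an answer. Protocol 9.2 bases outcomes up to 12 months on Core Treatment Phase data, which might imply on-treatment data, but its parenthesis describes this as the first 12 months per patient, so it does not settle the matter. One may also say that counting post-switch data is a legitimate choice. But under footnote z, Long-Term Follow-Up is by telephone, so no scheduled PCR follows the End of Treatment visit, and time to response takes the opposite position. The plan does not carry that choice through.

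**Conclusion.** The gap is real and limited. By their wording, MMR by 12 and 18 months and CCyR by 12 months accept a first response on a sample taken after a new anti-CML drug has started, and time to response contradicts them. These endpoints are secondary and carry no hypothesis test, so the harm is a possible upward bias in descriptive rates: 1.7 percentage points per misclassified responder at N = 60, in a number of patients that is probably small and that the documents do not let one estimate.

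Exposure of the primary endpoint is conditional on an End of Treatment sample being used as the Week 48 assessment. Under the assumed ±4-day window, uniform stopping times and 10 to 30% discontinuation by Week 48, at most about 0.5 to 1.6 of 60 patients could be in that position. The SAP should still close the question, because one such patient matters against a threshold of 21. The correction is worth making: it mends a stated counting rule, lowers bias in an uncontrolled trial, and leaves N, alpha and power unchanged.

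**What to change.** **(a) SAP 3.2, 5.3 and 6.2.** State that assessments on or after the start date of any new anti-CML therapy do not count as MMR, MR or CCyR response, observed or imputed, in any response-rate endpoint. Say that this includes an End of Treatment sample falling in the Week 48 window. Reconcile the protocol's 28-day extension for duration (9.2.2.3) with the on-treatment censoring in SAP 3.2.3, and use one meaning of on treatment throughout.

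**(b) Protocol 6.4 and footnotes p, s and t.** Ask that End of Treatment PCR, mutation and any required marrow samples be drawn before new anti-CML therapy where possible, as footnote h does for the ECG, and without delaying that therapy. The safety part of the visit stays where it is.

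**Cost.** (a) is a short SAP text change. It needs the start date of new therapy; Protocol Section 3 already follows initiation of further anticancer therapy. (b) is footnote wording and requires no additional sample. For early switchers the disease samples may fall on a different day from the safety visit, which can mean an extra attendance.
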